4.5.2 Required Observations for Cycles 2+, Cohort C

- a. Hx/Wt/Ht/BSA. Within 7 days prior to subsequent cycles and at the end of study treatment.
- b. Performance status. Prior to subsequent cycles and at the end of study treatment.
- c. Physical exam (including VS). Prior to subsequent cycles and at the end of study treatment.
- d. CBC/diff/platelets: Prior to subsequent cycles. If patients have Grade 4 neutropenia then CBCs should be checked every 3 to 4 days until recovery to Grade 3 or until meeting the criteria for dose limiting toxicity.
- e. Electrolytes including Ca⁺⁺. Prior to subsequent cycles.
- f. Creatinine, ALT, bilirubin. Prior to subsequent cycles.
- g. Disease evaluation, lumbar puncture, and evaluation of any sites of extramedullary disease. After Cycles 2, 4, 6, 9, 12, 16, 20, and 24. Please refer to [Section 10.4](#) for Confirmation of objective response by RECIST 1.1.
- h. Bone marrow evaluation. With Disease evaluation. If the institutional investigator has determined the patient has progressed based on clinical or laboratory evidence, he/she may opt not to confirm this finding on marrow pathology.
- i. Circulating tumor DNA. On Day 1 of Cycle 2, before Cycle 7, and at the time of progression. See [Section 7.3.2](#) for details.
- j. Tumor tissue submission. Submission of tumor tissue from any bone marrow evaluation while on study is required. Submission of tumor tissue from any biopsy after progression is optional. See [Section 7.3.1](#) for details.

- k. Patient diary. Uploaded into RAVE at the end of each cycle. See [Appendix VII-A](#) and [Appendix VII-B](#) for details.
- l. Pregnancy test. Prior to subsequent cycles. Sexually active patients must use an acceptable method of birth control.
- m. Cerebral spinal fluid (CSF) cell count and differential. With disease evaluation.
- n. Neurocognitive assessments. 6 months (\pm 4 weeks) after enrollment, 12 months (\pm 4 weeks) after enrollment, 24 months (\pm 4 weeks), and 4-5 years after enrollment. See [Section 3.1.7](#) and [Appendix XI](#) for details.

This listing only includes evaluations necessary to answer the primary and secondary aims. OBTAIN OTHER STUDIES AS REQUIRED FOR GOOD CLINICAL CARE.

Comments

(Include any held doses, or dose modifications)

4.5.3 Treatment Details: Cycles 2+, Cohort C**Methotrexate OR Cytarabine OR Triples (Methotrexate/Hydrocortisone/Cytarabine): Intrathecal**

Days: -3 to 1

Dose: A single dose of IT therapy will be administered with each cycle 2+.

Note that patients who do not clear their CSF by the end of Cycle 1 will be removed from protocol therapy.

Methotrexate

Patients with ALL ONLY.

| Age (yrs) | Dose |
|------------------|-------------|
| <1 | 7.5 mg |
| 1-1.99 | 8 mg |
| 2-2.99 | 10 mg |
| 3-8.99 | 12 mg |
| ≥ 9 | 15 mg |

Cytarabine

Patients with AML ONLY.

| Age (yrs) | Dose |
|------------------|-------------|
| < 1 | 20 mg |
| 1 – 1.99 | 30 mg |
| 2 – 2.99 | 50 mg |
| ≥ 3 | 70 mg |

Methotrexate (MTX)/Hydrocortisone (HC)/Cytarabine (ARAC)Patients with ALL who were CNS 3 (see [Section 10.8](#)) at enrollment may receive either methotrexate or triples at their physician's discretion.

| Age (yrs) | Dose |
|------------------|--------------------------------------|
| <1 | MTX: 7.5 mg, HC: 7.5 mg, ARAC: 15 mg |
| 1-1.99 | MTX: 8 mg, HC: 8 mg, ARAC: 16 mg |
| 2-2.99 | MTX: 10 mg, HC: 10 mg, ARAC: 20 mg |

| | |
|--------|------------------------------------|
| 3-8.99 | MTX: 12 mg, HC: 12 mg, ARAC: 24 mg |
| ≥ 9 | MTX: 15 mg, HC: 15 mg, ARAC: 30 mg |

Larotrectinib: Oral/Nasogastric/Gastrostomy

Days: 1 - 28

Dose: 100 mg/m²/dose BID (maximum of 100 mg/dose BID).

Only use larotrectinib provided for investigational use specifically for ADVL1823.

Note that this study will enroll very young children, but the dose will be based on body surface area for all patients regardless of age.

Larotrectinib capsules should not be opened and must be swallowed whole. If vomiting occurs following dosing, doses should NOT be repeated and the next dose should be administered at the regularly scheduled time. If a dose is missed, it may be administered if there is at least 8 hours remaining until the next scheduled dose. Liquid formulation is also available and may be administered orally or via NG- or G-tube.

Drug doses should be adjusted based on the BSA calculated from height and weight measured within 7 days prior to the beginning of each cycle and according to the dosing nomogram (see [Appendix X-A](#)). Doses of larotrectinib capsules should be rounded to the nearest 25 mg ([Appendix X-A](#)). Calculated dosing volumes of larotrectinib liquid formulation should be rounded to the nearest 0.1 mL (2 mg) for doses ≤ 45 mg (in oral syringes ≤ 3 mL) and 0.2 mL (4 mg) for doses > 45 mg (in 5-10 mL oral syringes) for the actual deliverable dose ([Appendix X-B](#)).

All patients taking larotrectinib must complete a patient diary ([Appendix VII-A](#) and [Appendix VII-B](#)).

See [Section 5.0 for Dose Modifications based on Toxicities](#).

Patients will have disease evaluation at the end of Cycles 2, 4, 6, 9, 12, 16, 20, and 24. Patients with progressive disease, treatment failure, or relapse at any time will discontinue protocol therapy.

For all other patients, the next cycle starts on Day 29 or when the criteria in [Section 4.1.3](#) are met (whichever occurs later). Patients achieving a response may discontinue protocol therapy at their physician's discretion to receive consolidative therapy (e.g., transplant).

5.0 DEFINITIONS AND DOSE MODIFICATION FOR TOXICITY

All dose modifications should be based on the worst preceding toxicity. The severity of adverse events will be graded utilizing the NCI CTCAE, Version 5.

5.1 Definition of Dose-Limiting Toxicity (DLT)

DLT will be defined as any of the following events that are possibly, probably or definitely attributable to protocol therapy.

Dose limiting hematological and non-hematological toxicities are defined differently.

5.1.1 Non-Hematological Dose-Limiting Toxicity

5.1.1.1 Any Grade 3 or greater non-hematological toxicity with the specific exception of:

- Grade 3 fatigue, nausea, or vomiting of < 3 days duration
- Grade 3 ALT/AST/GGT that return to levels that meet initial eligibility criteria within 7 days of study drug interruption and that do not recur upon re-challenge with study drug. Note: For the purposes of this trial the ULN for ALT is defined as 45 U/L and the ULN for AST as 50 U/L. See [Appendix XII](#) for values that represent thresholds between CTCAE grades.
- Grade 3 or 4 total bilirubin elevation in infants who enrolled with physiologic jaundice and in patients with leukemia. For such patients, only the conjugated (direct) bilirubin will be considered a dose limiting toxicity.
- Grade 3 or 4 fever
- Grade 3 infection < 5 days duration
- Grade 3 weight gain
- Grade 3 hypophosphatemia, hypokalemia, hypocalcemia and/or hypomagnesemia responsive to oral supplementation

5.1.1.2 Any Grade 2 non-hematological toxicity that persists for ≥ 7 days and is considered sufficiently medically significant or sufficiently intolerable by patients that it requires treatment interruption will be considered a dose limiting toxicity.

- Grade 2 allergic reactions that necessitate discontinuation of study drug will not be considered a dose-limiting toxicity.

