2.7.1 Rationale for Extending Neurocognitive Assessments until 5 Years after Enrollment

ADVL1823 has now completed accrual and demonstrated that larotrectinib was highly active in patients with newly diagnosed infantile fibrosarcoma and other NTRK-fusion positive sarcomas.⁴⁷ ADVL1823 incorporated neurocognitive assessments for the first 2 years after enrollment. Compliance with these assessments has been high, but given the young age of patients enrolled to this study (median age at enrollment was 8 months), there are limitations in the ability to fully detect any potential neurocognitive late effects within 2 years of

enrollment, as the median age of patients at this timepoint is < 3 years. As such, we will add an additional timepoint for assessment of neurocognitive outcomes at 4-5 years after enrollment (prior to the 5th anniversary at which point patients are off study). We have included a relatively broad time window to simplify data collection during a routine visit for these patients, many of whom may not be receiving any therapy.

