3.2.6 Organ Function Requirements

3.2.6.1 Adequate Bone Marrow Function Defined As:

- a. For patients with solid tumors without known bone marrow involvement:
 - Peripheral absolute neutrophil count (ANC) $\geq 1000/\text{mm}^3$
 - Platelet count $\geq 100,000/\text{mm}^3$ (transfusion independent, defined as not receiving platelet transfusions for at least 7 days prior to enrollment)
 - Hemoglobin $\geq 8.0 \text{ g/dL}$ at baseline (may receive RBC transfusions)
- b. Patients with solid tumors with known bone marrow metastatic disease will be eligible for study provided they meet the blood counts in Section 3.2.6.1.a (may receive transfusions provided they are not known to be refractory to red cell or platelet transfusions). These patients will not be evaluable for hematologic toxicity.
- c. For patients with leukemia:
 - Platelet count $\geq 20,000/\text{mm}^3$ (may receive platelet transfusions).
 - Hemoglobin $\geq 8.0 \text{ g/dL}$ at baseline (may receive RBC transfusions)
 - These patients must not be known to be refractory to red cell or platelet transfusion.

3.2.6.2 Adequate Renal Function Defined As:

- a. Creatinine clearance or radioisotope GFR $\geq 70 \text{ mL/min}/1.73 \text{ m}^2$ **or** a serum creatinine based on age/sex as follows:

| Age | Maximum Serum Creatinine (mg/dL) | |
|-------------------------|----------------------------------|--------|
| | Male | Female |
| 1 month to < 6 months | 0.4 | 0.4 |
| 6 months to < 1 year | 0.5 | 0.5 |
| 1 to < 2 years | 0.6 | 0.6 |
| 2 to < 6 years | 0.8 | 0.8 |
| 6 to < 10 years | 1 | 1 |
| 10 to < 13 years | 1.2 | 1.2 |
| 13 to < 16 years | 1.5 | 1.4 |
| $\geq 16 \text{ years}$ | 1.7 | 1.4 |

The threshold creatinine values in this Table were derived from the Schwartz formula for estimating GFR utilizing child length and stature data published by the CDC.⁴⁸

- For patients <1 month of age, serum creatinine levels must be <1.5x the treating institution's creatinine ULN for patients <1 month of age or the creatinine clearance or radioisotope GFR must be $\geq 70 \text{ mL/min}/1.73 \text{ m}^2$.

3.2.6.3 Adequate Liver Function Defined As:

- i. Patients with solid tumors:
 - Bilirubin (sum of conjugated + unconjugated) $\leq 1.5 \times$ upper limit of normal (ULN) for age. After approval of the study chair or designee, infants with a higher total bilirubin due to physiologic or breast milk jaundice are eligible if the conjugated (direct) bilirubin is ≤ 2 mg/dL.

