5.3 Dose Modifications for Non-Hematological Toxicity

- 5.3.1 If a patient experiences non-hematological dose-limiting toxicity as defined in [Section 5.1.1](#), the treatment will be held. When the toxicity resolves to meet eligibility parameters or baseline within 21 days of drug discontinuation, the patient may resume treatment with a dose reduction. The first dose reduction will be to 75 mg/m²/dose BID (cap of 75 mg/dose BID), the second dose reduction will be to 50 mg/m²/dose BID (cap of 50 mg/dose BID), and a third dose reduction of 25 mg/m²/dose BID (cap of 25 mg/dose BID). Doses reduced for toxicity will not be re-escalated, even if there is minimal or no toxicity with the reduced dose, except as required due to patient growth to maintain the same BSA-based dose.
- 5.3.2 If toxicity does not resolve to meet eligibility or baseline parameters within 21 days of drug discontinuation, the patient must be removed from protocol therapy.
- 5.3.3 Up to 3 dose reductions are permitted per patient. If a dose-limiting toxicity recurs in a patient who has resumed treatment following three dose reductions, the patient

must be removed from protocol therapy.

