11.4 Reporting Requirements for Specialized AEs

11.4.1 Baseline AEs

Although a pertinent positive finding identified on baseline assessment is not an AE, when possible it is to be documented as “Course Zero” using CTCAE terminology and grade. An expedited AE report is not required if a patient is entered on a protocol with a pre-existing condition (e.g., elevated laboratory value, diarrhea). The baseline AE must be re-assessed throughout the study and reported if it fulfills expedited AE reporting guidelines.

- a. If the pre-existing condition worsens in severity, the investigator must reassess the event to determine if an expedited report is required.
- b. If the AE resolves and then recurs, the investigator must re-assess the event to determine if an expedited report is required.
- c. No modification in grading is to be made to account for abnormalities existing at baseline.

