APPENDIX XII: TOXICITY-SPECIFIC GRADING**Bilirubin**

| | |
|----------|--------------------------|
| Grade 1: | > ULN - \leq 1.5 x ULN |
| Grade 2: | > 1.5 x ULN – 3.0 x ULN |
| Grade 3: | > 3.0 x ULN – 10.0 x ULN |
| Grade 4: | > 10.0 x ULN |

ALT: For the purpose of this study, the ULN for SGPT is 45 U/L regardless of baseline.

| | |
|----------|---------------------------|
| Grade 1: | > 45 U/L - \leq 135 U/L |
| Grade 2: | 136 U/L – 225 U/L |
| Grade 3: | 226 U/L – 900 U/L |
| Grade 4: | > 900 U/L |

AST: For the purpose of this study, the ULN for SGOT is 50 U/L regardless of baseline.

| | |
|----------|---------------------------|
| Grade 1: | > 50 U/L - \leq 150 U/L |
| Grade 2: | 151 U/L – 250 U/L |
| Grade 3: | 251 U/L – 1000 U/L |
| Grade 4: | > 1000 U/L |

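### The bilirubin DLT exemption omits infants with breast milk jaundice, whom eligibility admits on the same terms as those with physiologic jaundice

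*Combined protocol and SAP*

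**What the plan says.** **Entry.** For solid tumors, section 3.2.6.3 caps total bilirubin at 1.5 x ULN for age. It then makes one exception: "infants with a higher total bilirubin due to physiologic or breast milk jaundice are eligible", subject to approval by the study chair or designee and conjugated bilirubin of at most 2 mg/dL. Both causes of jaundice appear in the same sentence with the same conditions. No upper limit on total bilirubin is set for these infants.

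**DLT definition.** Section 5.1 sets the attribution condition: "DLT will be defined as any of the following events that are possibly, probably or definitely attributable to protocol therapy". Section 5.1.1.1 then makes every non-hematological event of Grade 3 or higher a DLT unless it is on a list of specific exceptions. The bilirubin item on that list is "Grade 3 or 4 total bilirubin elevation in infants who enrolled with physiologic jaundice and in patients with leukemia"; for those patients only conjugated bilirubin counts.

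**Grading.** Appendix XII defines Grade 3 bilirubin as "> 3.0 x ULN – 10.0 x ULN", with Grade 4 above that. Grades are multiples of ULN, not of the patient's own baseline.

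**Consequence.** Under section 5.3.1 the drug is held. It may be resumed, at a reduced dose, if "the toxicity resolves to meet eligibility parameters or baseline within 21 days of drug discontinuation". The first reduction is from 100 to 75 mg/m²/dose, and "Doses reduced for toxicity will not be re-escalated, even if there is minimal or no toxicity with the reduced dose", apart from adjustment for growth.

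**The concern.** Eligibility treats the two kinds of jaundice as interchangeable. The DLT rule does not, and the protocol gives no reason for the difference. The exemption exists because a raised total bilirubin with acceptable conjugated bilirubin, in an infant who enrolled with jaundice, is poor evidence of drug toxicity. That reasoning applies equally to both groups admitted under 3.2.6.3.

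What is at stake is the dosing of individual infants and the consistency of DLT classification. An infant with breast milk jaundice could lose drug exposure for a laboratory pattern that the protocol expressly disregards in an otherwise identical infant.

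**Working it through.** The plan states no figure to reproduce here. The check is a comparison of clauses, followed by simple arithmetic on the thresholds.

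**1. The clauses side by side**

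| Step | Physiologic jaundice | Breast milk jaundice |
|---|---|---|
| Entry above 1.5 x ULN (3.2.6.3) | Allowed with approval and conjugated ≤ 2 mg/dL | Allowed on the same terms |
| On-treatment total > 3.0 x ULN (Appendix XII) | Grade 3 | Grade 3 |
| Exempt from DLT on total bilirubin (5.1.1.1) | Yes; conjugated only | Not named |
| DLT if at least possibly related and conjugated not dose-limiting (5.1) | No | Yes |
| Action (5.3.1) | None | Hold; resume only at a reduced dose |

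**2. Whether another section closes the gap.** The documents mention breast milk jaundice only in 3.2.6.3. Nothing defines physiologic jaundice as including it, and 3.2.6.3 lists the two as alternatives.

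**3. How far above entry the value must be.** Grade 3 threshold / standard entry limit = 3.0 x ULN / 1.5 x ULN = 2.0. The total must exceed twice the standard limit before the two groups separate.

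**4. Size of the dose effect.** First reduction = (100 − 75) / 100 = 25%.

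**5. Illustration, under an assumed ULN.** The documents say only that ULN is for age, so I assume 1.0 to 1.2 mg/dL.

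- Grade 3 then starts above 3.0 x 1.0 = 3.0 mg/dL to 3.0 x 1.2 = 3.6 mg/dL.
- An infant with total 5.0 and conjugated 0.5 mg/dL is at 5.0 / 1.2 = 4.2 to 5.0 / 1.0 = 5.0 x ULN, which is Grade 3. This is a DLT or not depending only on which jaundice was recorded at entry.
- If the laboratory's ULN for age is 5.0 / 3.0 = 1.67 mg/dL or more, the same value is not Grade 3 and neither infant has a DLT.

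The ULN determines which values are caught. The difference between the groups remains for any total above 3.0 x ULN.

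**6. What does not follow.**

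- The pre-dose value is not itself an event. Section 11.4.1 opens with "Although a pertinent positive finding identified on baseline assessment is not an AE". It also says that grades are not adjusted for baseline abnormality, so a later event is still graded against ULN.
- Removal from therapy for a value that has returned to its entry level does not follow, because 5.3 accepts recovery to baseline.
- The Bayesian rule in 9.3.1 does not list bilirubin, and the response definitions and two-stage rule do not use DLT status.

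**The case against.** The strongest objection is attribution. These infants were admitted precisely because a non-drug cause of their raised bilirubin had been accepted before the first dose. An investigator seeing a continued high total with low conjugated bilirubin would ordinarily call it unrelated or unlikely, and then there is no DLT. This reduces the problem but does not remove it. The bar is only that the event be possibly related, section 2.2.2 names the liver as the most sensitive organ in animal toxicology, and the same attribution test applies to infants with physiologic jaundice. If attribution were enough, their exemption would not have been needed.

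Three further points have some force.

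- **Baseline.** Because 3.2.6.3 sets no ceiling on total bilirubin, an infant may enter above 3.0 x ULN. An unchanged value is then the baseline condition rather than a new toxicity. That is right, and the point concerns on-treatment events judged at least possibly due to the drug, not unchanged entry values.
- **Grade 2.** Section 5.1.1.2 can make a persistent Grade 2 toxicity that requires interruption a DLT. The bilirubin exemption covers Grades 3 and 4 only, so the two groups do not clearly differ at Grade 2, and I make no claim there.
- **Use of the result.** Section 9 plans no DLT analysis. Toxicity is tabulated by type and worst grade, which is the same for both groups. This stands, and it is why the point is minor.

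Two readings of intent are possible: that physiologic jaundice was shorthand for both causes, or that the narrower exemption was deliberate caution. The text supports neither. If the first was meant, the correction makes the protocol say so. If the second was meant, a reason should be given.

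**Conclusion.** The inconsistency is real and follows directly from the text. Its practical weight is small. Four conditions must hold together: entry under the allowance for breast milk jaundice; on-treatment total bilirubin above 3.0 x ULN; conjugated bilirubin not itself dose-limiting; and attribution at least possible. Where all four hold, the infant has a hold and, on resuming, a 25% first reduction that an otherwise identical infant with physiologic jaundice would not have.

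The number of such infants is unknown and may be zero. Section 2.7.1 states that "ADVL1823 has now completed accrual" and gives a median age at enrollment of 8 months, so a provision aimed at early infancy probably concerned few patients. What remains is the classification of any DLT already recorded on total bilirubin and any reuse of this text. Nothing in the primary analysis changes.

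The conclusion rests on reading the two kinds of jaundice as distinct, as 3.2.6.3 does, and the exceptions in 5.1.1.1 as a closed list.

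**What to change.** In section 5.1.1.1, insert the three words *or breast milk* after *physiologic* in the bilirubin exception, so that it covers the same infants as 3.2.6.3.

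Then check the records of infants who needed chair or designee approval under 3.2.6.3. If any had a DLT classified on total bilirubin after entering with breast milk jaundice, report it together with the conjugated value and any resulting dose reduction.

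The cost is a three-word wording change and a record review limited to that small group. No new data and no change to the design are needed.

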5.1.2 Hematological dose limiting toxicity

5.1.2.1 Hematological dose limiting toxicity is defined as:

- a) In patients with solid tumors evaluable for hematological toxicity (see [Section 3.2.6.1a](#)),
 - Grade 4 thrombocytopenia (platelet count $< 25,000/\mu\text{L}$) or Grade 4 neutropenia, not due to malignant infiltration.
 - Grade 3 thrombocytopenia that persists for ≥ 7 days
 - Grade 3 thrombocytopenia requiring a platelet transfusion on two separate days within a 7-day period
 - Grade 3 thrombocytopenia with clinically significant bleeding

- b) In patients with leukemia, DLT will be defined as failure to recover a peripheral ANC > 500/ μ L and platelets > 20,000/ μ L without transfusion by 42 days after the first treatment day, not due to malignant infiltration.

Note: Grade 3 or 4 febrile neutropenia will not be considered a dose-limiting toxicity.

5.2 Dose Modifications for Hematological Toxicity

- 5.2.1 If a patient experiences hematological dose limiting toxicity as defined in [Section 5.1.2](#), the treatment will be held. Counts should be checked every 3-4 days during this time. If the toxicity resolves to meet eligibility parameters within 21 days of drug discontinuation, the patient may resume treatment with a dose reduction. The first dose reduction will be to 75 mg/m²/dose BID (cap of 75 mg/dose BID), the second dose reduction will be to 50 mg/m²/dose BID (cap of 50 mg/dose BID), and a third dose reduction of 25 mg/m²/dose BID (cap of 25 mg/dose BID). Doses reduced for toxicity will not be re-escalated, even if there is minimal or no toxicity with the reduced dose, except as required due to patient growth to maintain the same BSA-based dose.
- 5.2.2 If toxicity does not resolve to meet eligibility parameters within 21 days of drug discontinuation, the patient must be removed from protocol therapy.
- 5.2.3 Up to 3 dose reductions are permitted per patient. If hematological dose-limiting toxicity recurs in a patient who has resumed treatment following three dose reductions, the patient must be removed from protocol therapy.

